## 8.9. Analysis of Exploratory Efficacy Endpoints

Exploratory efficacy analyses for all populations include:

- Proportion of subjects with SVR12 by HCV genotype and presence of baseline NS5A and NS5B RAVs.
- Proportion of subjects with SVR24 by HCV genotype and presence of baseline NS5A and NS5B RAVs.
- Proportion of subjects with SVR4 by HCV genotype and presence of baseline NS5A and NS5B RAVs.
- The proportion of subjects achieving SVR24, analyzed using the same method as for SVR12.
- Proportion of emergence of NS5A and NS5B RAVs in subjects who experience virologic failure. Results will also be summarized by genotype.
- Proportion of baseline NS5A and NS5B RAVs in subjects who experience virologic failure. Results will also be summarized by genotype.
- Prevalence of specific baseline and treatment-emergent NS5A and NS5B RASs by genotype and by virologic failure at SVR12
- SVR12 will be estimated and presented with 95% CIs by demographics and/or baseline characteristics including prior HCV treatment and baseline viral load (baseline viral load will be categorized using the median as a low-high cut-off point).
- HCV RNA IU/ml log10 value will be tabulated by HCV genotype and the average change from baseline over time will be plotted.
- Qualitative HCV RNA results will be tabulated by HCV genotype over time
- Exposure-response relationships will be explored by scatter plots of drug exposure versus change in HCV RNA IU/ml log10 value.

## **9. SAFETY AND TOLERABILITY**

### **9.1. Overall Summary of Tolerability**

All adverse events will be coded according to the Medical Dictionary for Regulatory Activities (MedDRA) and will be summarized for the safety population. Only treatment-emergent adverse events (TEAE) will be summarized. Treatment emergent adverse events are those with start date/time within the treatment period, defined as the time from first study drug administration to 4 weeks post treatment. Events that occur after 4 weeks with relationship to study drug recorded as 'related' will also be considered as treatment emergent. If the AE onset date is missing or partial, the conventions described in Section **Error! Reference source not found.** will be used to determine if the event is treatment emergent.

Adverse event severity will be graded according to the Division of AIDS (DAIDS) Table for Grading the Severity of Adult and Pediatric Adverse Events, Version 2.1 dated July 2017.

An overall summary of adverse events will be presented and include tabulations (number and %, unless otherwise indicated) for the following:

- Subjects with at least one TEAE, overall and by worst grade
- Total number (number only) of TEAEs
- Deaths
- Subjects who discontinued study due to an AE
- Subjects who discontinued treatment due to an AE
- Subjects with a treatment related AE resulting in treatment discontinuation
- Subjects with a serious adverse event (SAE)
- Subjects with a treatment related SAE
- Subjects with a treatment related AE, overall and by worst grade
- All Adverse Events will be listed

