## 7.2. Routine Reporting

For the purposes of this study, all AEs (serious and non-serious) will be recorded in the eCRF from the time of informed consent until 4 weeks after the last dose of study drugs. All SAEs will be recorded from the time of informed consent until the end of the study.

During these periods, all AEs spontaneously reported by the subject, observed by the clinical staff, or elicited by general questioning will be recorded and reported in the eCRF.

Any AE which remains unresolved as of the last visit will require follow-up until the AE has been resolved, a reasonable explanation for its persistence found, or is deemed chronic or stable by the investigator. It is the investigator's responsibility to ensure subjects experiencing AEs receive appropriate follow-up, treatment where required, and that every action is well documented.

Classification of AEs will be performed by System Organ Class and Preferred Term using The Medical Dictionary for Regulatory Activities (MedDRA).

Electronic case report form procedures for AE and SAE reporting can be found in the eCRF completion guidelines. Paper SAE forms are to be used only if the Electronic Data Capture (EDC) system is unavailable.

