## 8.5. Safety Analyses

Study treatment exposure (such as treatment duration and total dose received) will be summarized with descriptive statistics.

Treatment-emergent AEs and graded laboratory abnormalities, defined as any new or worsening AE/laboratory parameter beginning on or after the first dose of study drugs through 4 weeks after the last dose, will be included in the analysis.

Incidence and frequency of subjects experiencing AEs, SAEs, AEs resulting in treatment discontinuation, and AEs resulting in study discontinuation will also be summarized. Adverse events will be coded using MedDRA. The incidence and frequency of subjects with treatment-emergent adverse events will be tabulated by primary SOC and PT. The tabulation of the number of subjects with treatment-emergent AEs will also be provided by grade and relationship to study drug.

Changes from baseline in laboratory tests and vital signs will be summarized. Laboratory abnormalities will be graded in accordance with the DAIDS severity scale where applicable. Shift tables for treatment-emergent laboratory abnormalities will be presented.

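### SAP 9.1 leaves out the protocol's worsening criterion for treatment-emergent AEs, so a non-serious AE that starts in screening and worsens on drug may be missing from the TEAE summaries

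*SAP*

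**What the plan says.** Protocol 8.5 describes the treatment-emergent set as "defined as any new or worsening AE/laboratory parameter beginning on or after the first dose of study drugs through 4 weeks after the last dose". A worsening event therefore counts alongside a new one.

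SAP 9.1 works from the start date: "Treatment emergent adverse events are those with start date/time within the treatment period", a period that opens at first dose and closes 4 weeks post treatment. It extends the late end: "Events that occur after 4 weeks with relationship to study drug recorded as 'related' will also be considered as treatment emergent". It then limits the tables: "Only treatment-emergent adverse events (TEAE) will be summarized".

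SAP 6.8.3 treats an AE with a wholly missing start date as treatment emergent. Where only month and year are known, it places the start no earlier than the first treatment date.

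Protocol 7.2 has AEs recorded "from the time of informed consent until 4 weeks after the last dose of study drugs", and the schedule of assessments marks AE collection at Screening. The same section leaves the mechanics of AE entry to the eCRF completion guidelines.

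**The concern.** The two documents define the same safety set differently, and SAP 9.1 does not say that it departs from the protocol. Screening may last 28 days, or 42 with sponsor approval, so AE records with a pre-dose start date can exist. If such an AE becomes more intense on drug and keeps its record, its start date still lies before first dose and the SAP's rule does not select it.

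Safety and tolerability are a primary objective and there is no control product, so the TEAE tables are the main safety summary. An omission of this kind acts in one direction: it can reduce the number of TEAEs and the worst grades shown, and cannot increase them. It also sits oddly beside SAP 9.5, which judges laboratory data by the shift from baseline to worst grade and so does count worsening.

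**Working it through.** No sample-size, power or rate calculation applies. The check is to apply both definitions to each kind of event, and then to look for any other rule that brings the disputed kind into the SAP's set.

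**Step 1. Both definitions, case by case**

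| Event | Protocol 8.5 | SAP 9.1 |
|---|---|---|
| Starts on drug | Counts | Counts |
| Condition from before consent, worsens on drug | Counts | Counts: protocol 7.1 makes the worsening itself the AE, so its onset is on drug |
| Starts between consent and first dose, no change on drug | Does not count | Does not count |
| Starts between consent and first dose, becomes serious on drug | Counts | Counts if the new SAE report required by protocol 7.3 carries the on-drug date |
| Starts between consent and first dose, non-serious, grade rises on drug, new record opened | Counts | Counts |
| **Same event, original record kept** | **Counts** | **Does not count** |
| Related event starting more than 4 weeks after treatment | Does not count | Counts |

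The sixth row is the conflict. The last row shows that the SAP is wider than the protocol elsewhere.

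**Step 2. Could another rule rescue the sixth row?**

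- The late-related rule in SAP 9.1 extends only the end of the period.
- The date rules in SAP 6.8.3 need a missing or partial date. A complete screening date is unaffected.
- Protocol 7.3 requires a new report when a worsening AE becomes serious. Protocol 7.1.1 separates severity from seriousness, so a grade 3 non-serious event is not covered.
- Protocol 7.1 treats worsening of a pre-existing condition as an AE. It does not say that an AE record already open is closed and re-entered with a new date.
- SAP 9.5 covers worsening of laboratory values through shift tables. What is left is clinical AEs.

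None of these brings the event in.

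**Step 3. Where the event would be missing, and where it would remain**

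Missing: the TEAE rows of SAP 9.1; the SAP 9.2 tables by organ class and term (all TEAEs, maximum severity, related, leading to discontinuation); and the TEAE rows of SAP 9.2.1.

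Remaining: the listing of all AEs in SAP 9.1 and the count of all AEs reported in SAP 9.2.1.

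Unclear: rows in SAP 9.1 worded for AEs rather than TEAEs, such as treatment discontinuation due to an AE and treatment-related AEs by worst grade. The sentence limiting summaries to TEAEs leaves their scope open.

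**Step 4. Size**

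The documents give neither the rate of screening-onset AEs nor the share that worsens, so no count can be derived. If all 280 planned subjects are dosed, one subject omitted from a row lowers that row by 1/280 = 0.36 percentage points, provided the subject has no other event in that row.

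**The case against.** The best reply is that the two definitions can be read together. In protocol 8.5 the word for onset governs both new and worsening events, so a worsening may be taken to have an onset of its own. Protocol 7.1 supports this by listing worsening of a concomitant illness among the things an AE may be. On this reading an on-drug worsening is an AE that starts on drug, and a start-date rule finds it. If the eCRF guidelines require a new record at each increase in grade, nothing is lost.

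Part of this stands. It settles the case of conditions that predate consent, and it makes the practical loss depend on a convention the documents do not show. It does not settle an AE already open at first dose, because neither document says that the record is split. If the SAP relies on such a convention, it should state it.

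A reader might infer three stronger things that the documents do not support:

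- *On-drug worsening vanishes from the safety report.* It does not: the event stays in the listing and the all-AE count, and laboratory and serious worsening have their own routes.
- *The SAP undercounts TEAEs overall.* The late-related and missing-date rules make it more inclusive than the protocol in other respects. Only this omission is one-directional.
- *The study pausing rules are weakened.* Protocol 5.6.3 does not refer to TEAE status, so SAP 9.1 cannot affect it.

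**Conclusion.** The conflict is real but narrow. It concerns non-serious clinical AEs with a known onset between consent and first dose that increase in grade on drug and keep their original record. These are treatment emergent under protocol 8.5 and not under SAP 9.1.

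Whether any event is lost in practice rests on one assumption: that the eCRF does not open a new record at worsening. The size cannot be derived and is probably small, given how many conditions must coincide. Nothing in the documents shows that the omitted events would be mainly of higher grade. The change is worth making because the SAP departs from the protocol on a primary objective without saying so, the omission can only lower TEAE counts, and there is no comparator arm.

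**What to change.** Add to the definition in SAP 9.1, keeping the late-related and missing-date rules as they are:

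> or an AE with onset before first dose that increases in grade on or after first dose through 4 weeks after last dose, summarised at its worst post-dose grade.

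Confirm in the eCRF completion guidelines how a grade increase is dated, or whether it opens a new record, and state that convention in the SAP. If increases are not dated, count an AE that began before first dose and is ongoing at first dose as treatment emergent when its worsening cannot be shown to precede dosing. This follows the cautious approach that SAP 6.8.3 takes to missing start dates.

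The SAP cost is one clause. The data cost depends on the eCRF: protocol 7.1.1 describes a severity rating for each AE and does not mention dated changes, so the fallback may be needed. It may bring in a few events that did not worsen on drug, and the tables will show slightly more TEAEs. If the database is already locked, SAP section 2 provides for noting the departure in the clinical study report.

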### **9.2. Adverse Event Preferred Term and Body/Organ System Summary Tables**

Adverse events will be coded by System Organ Class (SOC) and preferred term (PT) using the Medical Dictionary for Regulatory Activities (MedDRA). Summaries by SOC and PT will be provided for the following:

- TEAEs
- TEAEs by maximum severity
- Related TEAEs
- TEAEs leading to study discontinuation

- TEAEs leading to treatment discontinuation
- SAEs
- Deaths.

A table of the most common AEs ( $\geq 5\%$ ) will be presented by PT only with display from most common to least.

### **9.2.1. Summaries of Adverse Events for All Subjects**

An overall summary of AEs will be presented including:

- Number of AEs reported
- Number of TEAEs reported
- Number (%) of subjects with at least one TEAE
- Number (%) of subjects with at least one study drug-related TEAEs
- Number (%) of TEAEs by relationship to study treatment
- Number (%) of TEAEs by severity grades
- Number (%) of SAEs
- Number (%) of subjects with a TEAE leading to discontinuation from study drug
- Number (%) of subjects with a TEAE leading to discontinuation from study
- Number (%) of subjects with outcome of death

Frequency tables will be presented:

- Number (%) of subjects with TEAEs by system organ class (SOC) and preferred term (PT)
- Number (%) of subjects with drug-related TEAEs by SOC and PT

### **9.2.2. Missing and Partial AE Onset Dates**

Missing or partial AE start dates will be handled in accordance with section 6.8.3.

### **9.2.3. Summaries of for Serious Adverse Events (SAE), Adverse Event Dropouts, and Death**

An overall summary of AEs will be presented including:

- Number of serious AEs (SAEs)
- Number (%) of subjects with at least one SAE
- Number (%) of subjects with at least one study drug-related SAE
- Death and SAEs, if recorded during the study, will be listed.

## **9.3. Exposure**

Study drug exposure will be characterized by the following:

- Number of doses of both study drugs received will be tabulated
- Total amount of both study drugs received will be summarized.
- Number of subjects that are  $\geq 90\%$  compliant/ $< 90\%$  compliant.

## **9.4. Concomitant and Other Medications**

Concomitant medications (CM) are medications that are administered during the treatment-emergent period. If the (CM) onset date and/or end date is missing or partial, the conventions described in Section 6.8.2 will be used to determine if the medication is concomitant. Medications will be presented based on WHODRUG coding.

### **9.4.1. Missing and Partial Concomitant and Other Medication Start and Stop Dates**

Missing and partial dates for concomitant medications will be handled in accordance with section 6.8.2.

## **9.5. Routine Laboratory Data**

The statistical analysis will present results in standardized units. Continuous laboratory parameters will be summarized by means of descriptive statistics at each analysis visit. Actual values and changes from baseline will be tabulated separately.

Toxicity grades will be presented as cross-tabulations of the toxicity grades at the worse-case analysis visit versus the baseline toxicity. Numbers of subjects with treatment-emergent toxicity grades will also be shown. Shift tables (baseline to worst) will be presented. Laboratory toxicities will be graded according to the DAIDS criteria. Any laboratory abnormalities deemed clinically significant by the investigator will be recorded as Adverse Events.

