### **5.6.2. Individual Safety Stopping Rules**

Treatment will be discontinued in any subject who experiences any one of the following:

- Confirmed elevation of ALT and/or AST  $> 5 \times$  baseline or post-baseline nadir, and  $> 5 \times$  ULN
- Confirmed elevation of ALT and/or AST  $> 15 \times$  ULN
- Confirmed elevation of ALT and/or AST  $> 3 \times$  post-baseline nadir, is  $> 3 \times$  ULN, and total bilirubin  $> 2 \times$  ULN, without any alternative causes or reason for these elevations
- Confirmed new onset  $\geq$  grade 3 elevation in creatinine or decreased GFR  $< 30 \text{ mL/min}/1.73 \text{ m}^2$
- Any SAE or grade 4 AE (including any confirmed grade 4 laboratory abnormality reported as an AE) that are considered by the investigator to be related to study drugs, *Note: To warrant treatment discontinuation, a grade 4 laboratory abnormality should have clinical findings expected to be associated with the laboratory abnormality. Subjects with isolated asymptomatic laboratory abnormalities without any clinical correlations are allowed to remain on treatment with continued monitoring according to the preference of the investigator.*
- Pregnancy during treatment (i.e., in female study subjects)

A confirmed value is defined as one that is repeated at the next subsequent test. Any of the above laboratory results and all  $\geq$  grade 3 new onset laboratory abnormalities must be repeated as soon as possible, preferably within 48 hours upon reporting of the initial value.

Additional follow-up and medical care, beyond what is specified in the protocol, is described in Section 5.6.3.

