### **6.6. Laboratory Evaluations**

Clinical laboratory evaluations will be performed at specified visits. The following tests will be conducted only at Screening:

- Serologies for HCV (anti-HCV antibody), HBV (HBsAg), and HIV
- HbA1c

The following hematology, serum chemistry, coagulation, and urinalysis evaluations will be conducted at specified visits. The investigator or designee will assess each abnormal value to determine if it is clinically significant.

- Hematology: hematocrit, hemoglobin, platelet count, red blood cell count, white blood cell count with differential (absolute) including lymphocytes, monocytes, neutrophils, eosinophils, basophils, reticulocyte count, and mean corpuscular volume
- Coagulation: INR, prothrombin time
- Chemistry: ALT, AST, albumin, alkaline phosphatase, creatine kinase, creatinine, blood urea nitrogen or urea, eGFR calculation (MDRD), total bilirubin (reflex to direct bilirubin), glucose, amylase, lipase, potassium, sodium, bicarbonate, or total carbon dioxide
- Urinalysis: appearance, blood, color, glucose, leukocyte esterase, pH, protein, urobilinogen. Reflex to microscopic urinalysis if dipstick result is abnormal
- Serum or urine pregnancy test on females of childbearing potential

Laboratory samples will be sent to a central laboratory for analysis. However, for an individual visit(s), a second set of samples may be drawn by the investigator and sent to the site's local

laboratory to obtain “STAT” results, if needed for safety assessment, this includes Screening assessments.

The total volume of blood withdrawn during the course of the study should not exceed 500 mL per subject over any two-month period. However, it is possible that the total blood donation may be higher if repeat blood samples are required for safety assessments.

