### 6.7.4. Visit Windows

For the purposes of by-visit analyses for scheduled clinical assessments (i.e., excluding patient-reported assessments), visit windows for inclusion in the analysis are defined in Table 4. Note that the definition of baseline is provided in Section 6.

Early termination data will be mapped based on the scheduled Study Day of each scheduled visit as specified in the protocol schedule of events.

Visits assigned as “unscheduled” by labs for safety data and HCV RNA quantitation will be mapped based on the table below. If there is more than one unscheduled visit in a visit window, the visit closest to the target date will be used in by-visit analyses. If there is a tie between the number of days from the target date, the later visit will be used. Unscheduled visits that fall within the protocol-defined visit windows will be summarized in the by-visit analyses only if there is no scheduled visit available in the analysis visit window.

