### **6.7.5. Multiple Assessments**

If multiple assessments are obtained within a visit window for a subject, the value obtained closest to the target timepoint will be used. For any visit, no more than one value per subject will be included in an analysis. In the event of multiple observations that are equidistant from the target day (e.g., two observations on the same day or observations made in a similar time frame before and after target), the earliest value, based on date and time, will be selected.

Multiple efficacy assessments will follow the rules outlined in section 8.7.1.

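### SAP 9.5 can leave a higher repeat or unscheduled laboratory grade out of the worst-grade cross-tabulation, and does not say whether such results count in the shift tables

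*SAP*

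**What the plan says.** SAP 9.5 promises three laboratory grade outputs:

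- A cross-tabulation: "Toxicity grades will be presented as cross-tabulations of the toxicity grades at the worse-case analysis visit versus the baseline toxicity".
- A count: "Numbers of subjects with treatment-emergent toxicity grades will also be shown".
- Shifts: "Shift tables (baseline to worst) will be presented".

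Only the first is tied to an analysis visit. None says which results are eligible, or over what period.

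Two SAP sections decide which value represents a visit. Section 6.7.4, with the windows in Table 4, is written for by-visit analyses and expressly maps unscheduled safety laboratory data. An unscheduled visit inside the protocol's own visit window "will be summarized in the by-visit analyses only if there is no scheduled visit available in the analysis visit window". Section 6.7.5 is wider: "For any visit, no more than one value per subject will be included in an analysis". It takes the value nearest the target day. Its only stated exception is efficacy, which is sent to SAP 8.7.1.

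The protocol generates extra samples. Under section 5.6.2, laboratory results that meet a stopping criterion and all new-onset abnormalities of grade 3 or higher "must be repeated as soon as possible, preferably within 48 hours upon reporting of the initial value". Under section 6.6, "for an individual visit(s), a second set of samples may be drawn by the investigator" and sent to the site's local laboratory when a fast safety result is needed. Protocol 8.5 defines treatment-emergent graded laboratory abnormalities as every new or worsened parameter from first dose through 4 weeks after the last dose.

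**The concern.** A worst-grade table should take the maximum over everything measured. Here the maximum appears to be taken over values already thinned to one per window, by a rule that ignores severity. The samples at risk are confirmatory repeats and draws prompted by a safety question, and these are more likely than routine samples to carry a peak.

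Safety and tolerability is the first-listed primary objective, and the trial has one arm. A reader of the report has no control group to show that a count of severe laboratory grades is too low. The loss would also leave the SAP table short of what Protocol 8.5 says will be counted.

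**Working it through.** No sample size, power or rate in the documents bears on this point, so there is no stated figure to reproduce. The check is of the data-selection rules.

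**Inputs.** Windows: SAP Table 4. Target days: Protocol Table 2. Last dose on Day 56, so EOT = 56, EOT+20 = 76, EOT+21 = 77, and 4 weeks after last dose = Day 84. In Protocol Table 2 the clinical laboratory row appears to run through Week 8 and early termination and then stop; its layout is partly broken in the text available.

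**Step 1: do repeats land in occupied windows?** Take repeats drawn 2 to 7 days after each planned sample (an assumed range).

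| Analysis visit | Window (days) | Planned lab | Repeat days | Window holding the repeat |
|---|---|---|---|---|
| Week 1 | 2–11 | 8 | 10–15 | Week 1, then Week 2 from Day 12 |
| Week 2 | 12–21 | 15 | 17–22 | Week 2, then Week 4 on Day 22 |
| Week 4 | 22–35 | 29 | 31–36 | Week 4, then Week 6 on Day 36 |
| Week 6 | 36–49 | 43 | 45–50 | Week 6, then Week 8 on Day 50 |
| Week 8 | 50–76 | 57 | 59–64 | Week 8 |

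The windows have no gaps from Day 2 to Day 76, and each has its own planned laboratory draw. If all visits are attended, every one of these repeats shares a window with a scheduled sample. From Day 77 no laboratory draw appears to be planned, so an unscheduled value can represent that window.

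**Step 2: which value is kept?** Two hypothetical cases:

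- Scheduled Day 29 is grade 3 and the repeat on Day 31 is grade 4. Distances from target are 0 and 2 days. Both 6.7.4 and 6.7.5 keep Day 29, and the subject is shown as grade 3.
- An unscheduled Day 24 draw is grade 3 and scheduled Day 29 is grade 1. Day 24 lies outside the protocol window of Day 29 ± 3 (Days 26–32), so the scheduled-first sentence in 6.7.4 does not literally reach it. Section 6.7.5 does: distances are 5 and 0 days, so Day 29 is kept and no grade 3 appears.

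**Step 3: direction.** If S is the set of selected results and A the set of all results over the same period, S is a subset of A, so max(S) ≤ max(A). The worst grade can be understated, never overstated.

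**Step 4: size.** The documents give no frequency. One affected subject among 280 is 1/280 = 0.36 percentage points.

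As an illustration only, a simulation took log10(ALT/ULN) with mean 0, assumed between-subject SD 0.35 and a repeat triggered at 5 × ULN. The proportion of triggered repeats above the value that triggered them was:

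| Assumed within-subject SD | No true rise | Rise of 0.1 log10 | Rise of 0.2 log10 |
|---|---|---|---|
| 0.1 | 0.327 | 0.596 | 0.842 |
| 0.2 | 0.215 | 0.335 | 0.483 |

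A higher value need not be a higher grade, so these are upper limits for grade loss under the assumptions.

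**Step 5: tie rules.** If two unscheduled draws on Days 27 and 31 are the only Week 4 results, each is 2 days from Day 29. Section 6.7.4 takes the later (Day 31) and 6.7.5 the earlier (Day 27).

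**The case against.** The strongest reply is that the SAP never orders this exclusion. The scheduled-first preference is confined to by-visit analyses, and a baseline-to-worst table is not one. The shift-table and treatment-emergent sentences in 9.5 carry no analysis-visit limit, and Protocol 8.5 points to all values. On that reading the current text already separates the two uses. This stands for the shift tables and counts, where the text is ambiguous. It does not clear the cross-tabulation, which is defined by analysis visit and falls under 6.7.5, where the one-value limit applies to any analysis and only efficacy is excepted.

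Further points on that side stand in part:

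- A scheduled value that triggers a repeat normally stays in the table, so a confirming repeat of the same grade changes nothing.
- Unscheduled results survive when the scheduled visit in the window was missed, from Day 77 on, and often after early stopping.
- Local samples under Protocol 6.6 mostly duplicate a visit sample. Neither document says whether they enter these tables.
- Protocol 7.1 requires abnormalities that lead to discontinuation of study drug to be recorded as adverse events, SAP 9.1 and 9.2 tabulate those, and the stopping rules do not use the laboratory tables.

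The adverse-event route is not a full substitute. Protocol 7.1 does not record abnormalities without clinical significance, records a syndrome in place of the laboratory result, and lets the event grade differ from the laboratory grade. Protocol 5.6.2 itself foresees isolated asymptomatic grade 4 results. SAP 9.5 promises no laboratory listing, whereas 9.6 lists all vital signs.

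**Conclusion.** The point holds as a possible loss, limited in scope. Between Day 2 and EOT+20, a repeat or unscheduled result can be left out of the worst-grade cross-tabulation when its window holds a scheduled sample. The reported grade is then too low if the omitted result has a higher grade than the one kept. This assumes that the cross-tabulation is programmed from 6.7.4 and 6.7.5 as written and that scheduled visits are attended.

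A reader might go further and infer that every required repeat is removed from all laboratory toxicity tables and that peak toxicity will therefore be understated. The documents do not support that. The analysis-visit wording covers one output of three. The repeat is mandatory, but 48 hours is a preference that runs from reporting of the first value. The size cannot be derived from the documents; 0.36 percentage points per affected subject is arithmetic on 280, not an estimate of how many there will be. Nor would a subject stopped for a liver-enzyme elevation vanish from the report, because the adverse-event tables would show the event.

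What remains deserves correction: a primary safety output rests on a rule that can err only in the favourable direction and does not match Protocol 8.5.

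**What to change.** In SAP 9.5, state that the worst post-baseline grade, the baseline-to-worst shifts and the treatment-emergent grade counts use all post-baseline results in the database (scheduled, unscheduled and repeat) from first dose through 4 weeks after the last dose. This matches the period in Protocol 8.5. State whether local laboratory results are included and, if so, how they are graded.

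In SAP 6.7.4 and 6.7.5, limit the one-value selection for safety laboratory data to by-visit descriptive summaries, and give one tie rule in place of the two that conflict.

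The cost is a few sentences and a small programming change. Central-laboratory repeats need no new data. The reported grades may become slightly less favourable.
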